5.3 Dose Adaptation

5.3.1 Dose Reduction

Intrapatient dose reduction is not allowed in this study.

5.3.2 Treatment Interruption

Treatment with pembrolizumab may be interrupted at the Investigators discretion depending on the type and severity of the toxicity encountered. Treatment is to be interrupted in the event of any of the toxicities listed in Table 3.

In the event of treatment interruption due to toxicity of more than 56 days, the decision to restart treatment or not should be discussed and agreed between the Investigator and Sponsor.

Table 3. Dose Modification and Toxicity Management Guidelines for Immune-related Adverse Events Associated with Pembrolizumab

General instructions:

- 1. Corticosteroid taper should be initiated upon AE improving to Grade 1 or less and continue to taper over at least 4 weeks.
- 2. For situations where pembrolizumab has been withheld, pembrolizumab can be resumed after AE has been reduced to Grade 1 or 0 and corticosteroid has been tapered. Pembrolizumab should be permanently discontinued if AE does not resolve within 12 weeks of last dose or corticosteroids cannot be reduced to ≤10 mg prednisone or equivalent per day within 12 weeks.
- **3.** For severe and life-threatening irAEs, IV corticosteroid should be initiated first followed by oral steroid. Other immunosuppressive treatment should be initiated if irAEs cannot be controlled by corticosteroids.

Toxicity	Grade*	Action taken with pembrolizumab	Toxicity management	Monitor and follow-up
Pneumonitis	Grade 2 Grade 3 or 4, or recurrent Grade 2	Withhold Permanently discontinue	Administer corticosteroids (initial dose of 1-2 mg/kg prednisone or equivalent) followed by taper	 Monitor participants for signs and symptoms of pneumonitis Evaluate participants with suspected pneumonitis with radiographic imaging and initiate corticosteroid treatment Add prophylactic antibiotics for opportunistic infections
Diarrhea / Colitis	Grade 2 or 3 Grade 4	Withhold Permanently discontinue	Administer corticosteroids (initial dose of 1-2 mg/kg prednisone or equivalent) followed by taper	 Monitor participants for signs and symptoms of enterocolitis (ie, diarrhea, abdominal pain, blood or mucus in stool with or without fever) and of bowel perforation (ie, peritoneal signs and ileus). Participants with ≥ Grade 2 diarrhea suspecting colitis should consider GI consultation and performing endoscopy to rule out colitis. Participants with diarrhea/colitis should be advised to drink liberal quantities of clear fluids. If sufficient oral fluid intake is not feasible, fluid and electrolytes should be substituted via IV infusion.
AST / ALT elevation or Increased bilirubin	Grade 2	Withhold	Administer corticosteroids (initial dose of 0.5- 1 mg/kg prednisone or equivalent) followed by taper	Monitor with liver function tests (consider weekly or more frequently until liver enzyme value returned to baseline or is stable
	Grade 3 or 4	Permanently discontinue	Administer corticosteroids (initial dose of 1-2 mg/kg prednisone or equivalent) followed by taper	

Protocol n° UC-0105/1612 - version n°10.0, November 22, 2020

Type 1 diabetes mellitus (T1DM) or Hyperglycemia	Newly onset T1DM or Grade 3 or 4 hyperglycemia associated with evidence of β-cell failure	Withhold	 Initiate insulin replacement therapy for participants with T1DM Administer anti-hyperglycemic in participants with hyperglycemia 	•	Monitor participants for hyperglycemia or other signs and symptoms of diabetes.
Hypophysitis	Grade 2 Grade 3 or 4	Withhold Withhold or permanently discontinue(1)	Administer corticosteroids and initiate hormonal replacements as clinically indicated.	•	Monitor for signs and symptoms of hypophysitis (including hypopituitarism and adrenal insufficiency)
Hyperthyroidism	Grade 2 Grade 3 or 4	Continue Withhold or permanently discontinue ⁽¹⁾	Treat with non-selective beta-blockers (eg, propranolol) or thionamides as appropriate	•	Monitor for signs and symptoms of thyroid disorders.
Hypothyroidism	Grade 2-4	Continue	Initiate thyroid replacement hormones (eg, levothyroxine or liothyroinine) per standard of care	•	Monitor for signs and symptoms of thyroid disorders.
Nephritis and Renal dysfunction	Grade 2 Grade 3 or 4	Withhold Permanently discontinue	 Administer corticosteroids (prednisone 1-2 mg/kg or equivalent) followed by taper. 	•	Monitor changes of renal function
Myocarditis	Grade 1 or 2 Grade 3 or 4	Withhold Permanently discontinue	Based on severity of AE administer corticosteroids	•	Ensure adequate evaluation to confirm etiology and/or exclude other causes
Severe skin reactions	Grade 1 or 2 Grade 3 or 4	Withhold Permanently discontinue Events that require permanently discontinuation include and not limited to: Stevens- Johnson syndrome (SJS) and toxic epidermal necrolysis (TEN)	Based on the severity of the adverse reaction administer corticosteroids	•	Monitor patients for suspected severe skin reactions and exclude other causes For signs or symptoms of SJS or TEN, refer the patient for specialized care for assessment and treatment. If SJS or TEN is confirmed, permanently discontinue pembrolizumab
All other immune- related AEs	Intolerable/ persistent Grade 2 Grade 3	Withhold or discontinue based on the type of event.	Based on type and severity of AE administer corticosteroids	•	Ensure adequate evaluation to confirm etiology and/or exclude other causes

	Events that require discontinuation include and not limited to: Gullain-Barre Syndrome,	
	encephalitis	
Grade 4 or recurrent	Permanently	
Grade 3	discontinue	

* Grade= NCI CTCAE version 4.0

(1) Withhold or permanently discontinue pembrolizumab is at the discretion of the investigator or treating physician.

NOTE: For participants with Grade 3 or 4 immune-related endocrinopathy where withhold of pembrolizumab is required, pembrolizumab may be resumed when AE resolves to ≤ Grade 2 and is controlled with hormonal replacement therapy or achieved metabolic control (in case of T1DM).

5.4 Treatment Termination

Treatment will be continued for a maximum of 24 months (or 35 cycles, whichever is longer), or until disease progression. Early treatment discontinuation may also occur at the initiative of either the patient or the investigator for any reason that would be beneficial to the patient. These reasons include, but are not limited to: unacceptable toxicity, intercurrent conditions that preclude continuation of treatment, or patient request. The reasons for treatment discontinuation are to be documented in the patient's medical record and reported in the eCRF.

Except in case of consent withdrawal, patient follow-up will continue for 12-months after discontinuation of IP in compliance with the protocol.

5.5 Second course (Re-challenge)

Recent studies have shown that patients with a clinical benefit (i.e. objective response or prolonged stable disease) from their first anti-PD (L) 1 treatment could benefit from retreatment with the same immunotherapy (Akamatsu, 2018; Giaj Levra, 2019; Gobbini, 2020). This retreatment would be more beneficial in patients who have previously shown prolonged clinical benefit (Akamatsu, 2018; Giaj Levra, 2019; Gobbini, 2020).

Therefore, all participants who reach the maximum treatment duration per protocol (24 months - 35 pembrolizumab cycles) and stop the pembrolizumab with a clinical benefit (prolonged stable disease, partial or complete response), may be eligible for up to an additional 1 year (approximately 17 cycles) of pembrolizumab treatment if they progress during their follow-up phase. This retreatment is termed the Second Course (or Rechallenge) of this study and is only available if the study remains open and the participant meets the following conditions:

- Had SD, PR, or CR and stopped study treatment after completion of 35 administrations (approximately 2 years) of study treatment, and
- Experienced an investigator-determined radiographic disease progression by RECIST 1.1 for solid tumours, RECIST v1.1 combined with biomarker assessment for patients with germ-cell cancer, the IPCG response criteria for patients with PCNSL, the 'Lugano' criteria for response assessment using the FDG-PET-CT 5-PS and assessment of EBV load for patients with NK/T Lymphoma after stopping initial treatment, and
- No new anticancer treatment was administered after the last dose of study treatment, and
- No other approved or experimental treatment options are available and
- The participant meets all of the safety parameters listed in the inclusion criteria and none of the safety parameters listed in the exclusion criteria.

During the second course, pembrolizumab will be administered and managed in the same way as the initial course, according to the Investigator Brochure and all the guidelines outlined above in section 5.

An objective response or disease progression that occurs during the Second course of pembrolizumab for a participant will not be taken into account in the primary analysis.

5.6 Assessment of Treatment Compliance

Study treatment will be administered by intravenous infusion by the Investigator at the Investigational site. Treatment compliance will be assessed via review of patient medical records.

5.7 Drug Packaging and Labelling

Pembrolizumab will be provided by the Sponsor and labelled appropriately as investigational product for this study in accordance with the specific requirements of this study, applicable Good Manufacturing Practices, and national regulations. Packaging will be performed by Merck Sharp & Dohme.

Pembrolizumab for intravenous infusion is formulated as a sterile, preservative-free, concentrate for solution for infusion at a concentration of 25 mg/mL, supplied in single-dose 4 mL vials.

5.8 Shipment, Storage Conditions and Accountability and Destruction

The IP supplies, provided by Merck Sharp & Dohme on behalf of the sponsor, will be distributed to the pharmacy at the investigational centre via a dedicated courier in accordance with the current Good Distribution Practices guidelines.

The pharmacist of the trial site will receive numbered treatment and will acknowledge receipt of each shipment by returning an acknowledgement of receipt form, duly completed, to the distributor.

Investigational product will be supplied to sites on a per-patient basis. An initial supply of IP will be shipped to sites following registration of the patient in the eCRF. Subsequent requests for resupply should be made to the Sponsor as described in the Pharmacy Manual.

The Investigator is responsible for a safe and proper handling and storage of the IP at the investigational centre (this task may be delegated to a qualified pharmacist). The IP must be stored in a locked facility with restricted access to the Investigator and authorized personnel, and under environmental conditions consistent with the drug manufacturer recommendations (Summary of Product Characteristics [SmPC] or IB). Investigational products must be stored in the dark at a temperature between 2°C and 8°C. Do not freeze. Temperature logs should be maintained to document adequate storage during the trial. In the event of temperature excursions outside the labelled storage conditions, affected IP supplies should be placed in quarantine. The Sponsor should be contacted to recommend further action to be taken and/or arrange for resupply.

The Investigator must ensure that IP is administrated only to patients enrolled in this trial. The IP must not to be used outside the context of the trial protocol.

The Investigator or the authorized staff must document the receipt, the dispensation, and the return or destruction of all IP received during this trial. Records of IP delivery to the investigational site, the inventory at the site, the use by each patient, and the return to the Sponsor or destruction by the site of all unused IP must be implemented and maintained by the Investigator or another appropriately trained individual at the investigational site. These records should record, at least; dates, quantities, and batch numbers of IP. Forms will be provided by the sponsor to ensure trial treatment accountability. This process will be monitored by the Sponsor Clinical Research Associate (CRA) during the trial.

All remaining unused IP will be collected and returned for destruction. The destruction will take place in the Investigator centre under the responsibility of the pharmacist in accordance with national regulatory requirements, and with prior formal agreement from the sponsor. A certificate of destruction, identifying concerned products, will be given to the sponsor.

5.9 Concomitant Treatments

All medications and therapies taken by the patients or administered to the patients at the onset of trial and all medication given in addition to the IP during the trial are considered as concomitant medications.

Medications or vaccinations specifically prohibited in the exclusion criteria or Section 5.9.2 are not allowed during the ongoing trial. If there is a clinical indication requiring treatment with one of these medications, discontinuation from trial therapy may be required. The investigator should discuss any questions regarding this with the Sponsor. The final decision on any supportive therapy or vaccination rests with the investigator and/or the subject's primary physician.

5.9.1 Authorized Concomitant Treatments

All treatments that the investigator considers necessary for a subject's welfare may be administered at the discretion of the investigator in keeping with the community standards of medical care. All concomitant medication will be recorded on the eCRF including all prescription, over-the-counter, herbal supplements, and IV medications and fluids. If changes occur during the trial period, documentation of drug dosage, frequency, route, and date may also be included on the eCRF.

All medications that may interact with pembrolizumab or may induce or potentiate pembrolizumab related adverse events (see Section 5.9.2 and the Investigator Brochure) should be recorded if received within 14 days before the first dose of IP and 30 days after the last dose of IP.

The investigator should instruct the patient to notify the study site about any new medications (including over-the-counter drugs and herbal/alternative medications) he/she takes after the start of study

treatment. Patients must be instructed not to take any additional medications (including over-the-counter products and herbal/alternative medications) during the trial without prior consultation with the investigator.

Patients may receive any medications that the Investigator deems to be medically necessary, except for those prohibited treatments listed in Section 5.9.2.

5.9.2 Prohibited Concomitant Treatments

Subjects are prohibited from receiving the following therapies during the Screening and Treatment Phase (including retreatment for post-complete response relapse) of this trial:

- Antineoplastic systemic chemotherapy or biological therapy
- Immunotherapy not specified in this protocol
- Chemotherapy not specified in this protocol
- Investigational agents other than pembrolizumab
- Radiation therapy
 - Palliative radiation therapy to a single symptomatic lesion or to the brain may be allowed, provided the lesion is not a target lesion for RECIST v1.1 evaluation and the need for therapy does not equate to progressive disease. Patients with PD must discontinue study treatment.
- Live vaccines within 30 days prior to the first dose of IP and while participating in the trial. Examples of live vaccines include, but are not limited to, the following: measles, mumps, rubella, varicella/zoster, yellow fever, rabies, Bacillus Calmette–Guérin (BCG), and typhoid vaccine
- Systemic glucocorticoids at a dose greater than prednisone 10 mg/day or equivalent (Appendix 4). The use of physiologic doses of corticosteroids may be approved after consultation with the Sponsor.
- Other medications described in the exclusion criteria (Section 4.2)

Subjects who, in the assessment by the investigator, require the use of any of the aforementioned treatments for clinical management should be removed from the trial. Subjects may receive other medications that the investigator deems to be medically necessary.

There are no prohibited therapies during the LTFU Phase.

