3 TRIAL DESIGN

3.1 Evaluation Criteria

3.1.1 Primary Endpoint

Objective response rate per cohort, defined as the percentage of patients in each cohort with a complete response (CR) or partial response (PR) measured at the first scheduled disease assessment following study treatment initiation (Day 84, ± 7 days) as assessed by an Independent Review Committee (IRC) according to (i) the Response Evaluation Criteria in Solid Tumours version 1.1. (RECIST v1.1; Eisenhauer, 2009; Appendix 1) for patients with solid tumours, (ii) RECIST v1.1 combined with biomarker assessment (Fizazi, 2014; Appendix 2) for patients with germ-cell cancer, (iii) the International PCNSL cooperative group (IPCG) response criteria (Abrey, 2005; Appendix 3), (iv) the 'Lugano' criteria for response assessment using the fluorodeoxyglucose-positron emission tomography-computed tomography (FDG-PET-CT) five-point scale (5-PS; Barrington, 2014; Cheson, 2014; Appendix 4) and assessment of *Epstein-Barr* virus (EBV) load.

Patients who withdraw from the study prior to this time point and patients with non-evaluable disease will be considered as 'non-responders'in the analysis.

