6 EVALUATION OF TREATMENT EFFICACY AND SAFETY

6.1 Efficacy Evaluation

Treatment efficacy will be evaluated in solid tumours by measuring changes in tumour size in response to treatment; measured by computed tomography (CT) scan or Magnetic Resonance Imaging (MRI) according to RECIST v1.1 (Appendix 1). Patients with germ-cell cancer will be evaluated via RECIST v1.1 combined with measurement of biomarkers (AFP, hCG, and LDH; Appendix 2). Patients with PCNSL will be evaluated by magnetic resonance imaging (MRI) according to IPCG response criteria (Appendix 3). For patients with NK/T lymphoma response will be assessed via the 'Lugano' criteria for response assessment using the 5-PS classification system of FDG-PET-CT (Appendix 4 NK/T-cell lymphoma patients with complete response will be further categorised as being in remission or not according to the detectable level of EBV in the blood.

Patients disease will be assessed at "baseline" (during the screening period) and then every 84 ± 7 days until documented PD, or death, whichever occurs first. Assessment of biomarkers in germ-cell cancer patients will be performed on Day 1 of each treatment cycle (after Cycle 1). Patients who discontinue IP treatment for reasons other than progression, death or consent withdrawal will continue to perform disease evaluations every 84 ± 7 days during the LTFU period until PD, or new antineoplastic therapy.

The primary evaluation endpoint is the ORR after the first disease assessment at 84 (± 7) days (i.e. following four cycles of therapy). Death or withdrawal of consent before this point will be considered as treatment failure in this analysis.

Secondary evaluation endpoints include PFS, OS, best response to treatment, time to response and duration of response (see Section 3.1)

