6.1.1 Independent Review Committee

In addition to the Investigators assessment of response, a central evaluation of disease response will be performed by an IRC for all patients to confirm the response after the first disease assessment at 84 (± 7) days and each reported complete response.

The interim analysis of ORR in each cohort will be performed using the Investigator's assessment of response after the 10 first patients eligible have been enrolled in order to test for futility according to the two-stage Bayesian enrichment design (Section 10.2).

The IRC and Investigators' assessment of response will be used for the analysis of efficacy endpoints in the final study report. Comparisons between Investigator and IRC results will also be reported.

The IRC will comprise of experts in each cohort pathology. The IRC will be provided with recordings of each scheduled CT scan or MRI exam (DICOM format) as well as the results of any other clinical, biological, or radiological disease assessments performed. Disease evaluation will be performed according to the schedule and methods described in a separate IRC charter.

Note: Treatment decisions are to be made by the Investigator, based on their assessment of patient response.

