7.2.8.1 Disease Progression: Special Considerations for First Disease Evaluation

In some patients, immune-related response patterns can be characterized by an initial increase in size of tumour lesions before any subsequent decrease in tumour burden. In order to avoid prematurely interrupting the patients' treatment, the following guidelines should be observed.

At the first disease evaluation only (i.e. Day 84, \pm 7 days): In the event that the patient shows an increase in lesion size consistent with RECIST v1.1 or IPCG criteria for disease progression, the investigator may also consider the signs of clinical deterioration when deciding how to manage the situation:

- If the patient presents with signs and symptoms that could be related to disease progression: the patient is to be considered as having progressive disease and is to be withdrawn from treatment
- If the patient presents no clinical signs or symptoms associated with disease progression and the investigator suspects an immune-related response: treatment may be continued at the investigators discretion. In this case a follow-up clinical and radiological assessment performed within 28 days (± 7 days). If at this follow-up assessment the disease is evaluated as stable or responding according to RECIST v1.1 or IPCG response criteria, treatment may be continued and the patient will remain on study. If radiological disease progression is confirmed by this second evaluation however, the treatment will be discontinued (regardless of clinical status) and the appropriate end of treatment evaluations performed.

For the purposes of analysis, the results of both the initial (Day 84) disease assessment and follow-up disease assessment should be recorded in the eCRF. In all cases, evaluation of response will be made according to RECIST criteria base on radiological measurement.

For time to event analyses, the date of disease progression will be considered as the date of the initial evaluation at which disease progression was suspected (as per RECIST / IPCG recommendations) regardless of the clinical decision taken.

If the criteria for disease progression are met at a time point later than Day 84, the patient is to be withdrawn from treatment, regardless of clinical status. No confirmation of PD is required in this case.

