 total protein may have prognostic importance, the value of CSF total protein after therapy is unknown.
- At the time a CR is determined, the patient should have discontinued use of all corticosteroids for at least 2 weeks. Rare exceptions may be made for those patients receiving corticosteroids for another diagnosis (eg, panhypopituitarism).

Unconfirmed complete response (CRu) includes those patients who fulfill the criteria for CR with the following features/limitations:

- Any patient who fulfills all criteria for CR but continues to require corticosteroid therapy at any dose should be considered an unconfirmed CR. This is critical because corticosteroids may be oncolytic in treating occult tumor. In addition, corticosteroids may decrease gadolinium enhancement on MRI.
- Some patients will have a small but persistent enhancing abnormality on MRI related to biopsy or focal hemorrhage. It is often difficult to ascertain whether this represents a residual nidus of tumor or scar tissue. Adjunctive radiologic studies such as single-photon emission computed tomography or positron emission tomography may be helpful, but often the nature of these abnormalities may only be determined by observing the patient with serial scans. If the type of abnormality does not change

or slowly involutes over time without therapy and corticosteroids, it is reasonable to categorize it as a CR.

 Patients with a persistent minor abnormality on follow-up ophthalmologic examination (persistent nonmalignant cells in the vitreous, alteration of the retina/optic nerve that is not consistent with tumor infiltration) may be considered a CRu if this abnormality is unlikely to represent ocular lymphoma.

Partial response (PR) requires all of the following:

- A ≥ 50% decrease in the contrast-enhancing lesion seen on MRI as compared with baseline imaging.
- Corticosteroid dose is irrelevant to the determination of PR.
- Ophthalmologic examination should show a decrease in the vitreous cell count or retinal/optic nerve
 cellular infiltrate but may continue to show persistent malignant or suspicious cells. Color photos of
 the posterior pole of the eye should be obtained to document improvement in retinal/optic nerve
 infiltrates.

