Appendix 4: Lugano Classification of Response For NK/T-cell Lymphoma

Full article available at: http://jco.ascopubs.org/

Five-point scale of fluorodeoxyglucose (FDG) uptake measured by PET-CT⁶.

The 5-PS scores the most intense uptake in a site of initial disease, if present, as follows:

Score	Description
1	No uptake
2	Uptake ≤ mediastinum
3	Uptake> mediastinum but ≤ liver
4	Uptake moderately higher than liver
5	Uptake markedly higher than liver and/or new lesions
X	New areas of uptake unlikely to be related to lymphoma

Criteria for FDG-PET-CT based response assessment

Response	Site	Criteria
Complete	Lymph nodes and	Score 1, 2, or 3* with or without a residual mass on 5PS [†]
metabolic	extra lymphatic	It is recognized that in Waldeyer's ring or extranodal sites with
response	sites	high physiologic uptake or with activation within spleen or marrow (eg, with chemotherapy or myeloid colony-stimulating factors), uptake may be greater than normal mediastinum and/or liver. In this circumstance, complete metabolic response may be inferred if uptake at sites of initial involvement is no greater than surrounding normal tissue even if the tissue has high physiologic uptake
	New lesions Bone marrow	None No evidence of FDG-avid disease in marrow
Partial metabolic	Lymph nodes and extra lymphatic	Score 4 or 5 [†] with reduced uptake compared with baseline and residual mass(es) of any size
response	sites	At interim, these findings suggest responding disease
	New lesions Bone marrow	At end of treatment, these findings indicate residual disease None Residual uptake higher than uptake in normal marrow but reduced compared with baseline (diffuse uptake compatible with reactive changes from chemotherapy allowed). If there
		are persistent focal changes in the marrow in the context of a nodal response, consideration should be given to further evaluation with MRI or biopsy or an interval scan
No metabolic response	Target nodes/nodal masses, extranodal lesions	Score 4 or 5 with no significant change in FDG uptake from baseline at interim or end of treatment
	New lesions Bone marrow	None No change from baseline
	DOILE IIIGITOW	INO GHALIYE HOTH DASEIILE

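### The lesion condition on palliative radiotherapy in 5.9.2 names only RECIST v1.1 target lesions, so it excludes nothing in cohort 3 (IPCG), nor in cohort 7 (Lugano) when the irradiated site is the sole or most intense one

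*Protocol*

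**What the plan says.** **The exception.** Section 5.9.2 lists radiotherapy among the treatments prohibited in the screening and treatment phases, then makes one exception: "Palliative radiation therapy to a single symptomatic lesion or to the brain may be allowed". The exception carries two conditions, one on the lesion and one on progression: "provided the lesion is not a target lesion for RECIST v1.1 evaluation and the need for therapy does not equate to progressive disease". The section adds that patients with progression must stop study treatment. It closes by saying that subjects who need one of the listed treatments should be removed from the trial.

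**How response is assessed in the two cohorts concerned.**
- Cohort 3: section 6.1 states that "Patients with PCNSL will be evaluated by magnetic resonance imaging (MRI) according to IPCG response criteria". Under Appendix 3 a partial response requires at least a 50% "decrease in the contrast-enhancing lesion seen on MRI as compared with baseline imaging".
- Cohort 7: assessment is by Lugano on FDG-PET-CT. Appendix 4 says that "The 5-PS scores the most intense uptake in a site of initial disease", and a partial metabolic response rests on reduced uptake against baseline.

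**Who counts as a non-responder.** Section 3.1.1 names "Patients who withdraw from the study prior to this time point and patients with non-evaluable disease", and 10.2.1 repeats this. Sections 6.1 and 10.4 add death, withdrawal of consent and loss to follow-up.

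**Who assesses.** The primary endpoint uses the IRC, but "The interim analysis of ORR in each cohort will be performed using the Investigator's assessment of response" (section 6.1.1).

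**The concern.** The lesion condition exists to keep local treatment away from the lesions on which response is judged. It works in the five RECIST-based cohorts. In cohorts 3 and 7 the response criteria contain no RECIST target lesion, so the condition is met whatever is irradiated. In cohort 3 the named permitted field, the brain, is the organ whose enhancing lesion decides the response.

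The primary objective is response to pembrolizumab given alone, in small single-arm cohorts. If radiotherapy shrinks the assessed lesion, or lowers the uptake of the site that sets the five-point score, the patient can be recorded as a responder at Day 84 with the protocol followed exactly. The error runs in one direction only: it can raise the ORR but not lower it.

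**Working it through.** **Step 1. What the conditions exclude, cohort by cohort.**

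| Layer in 5.9.2 | RECIST-based cohorts | Cohort 3 (IPCG) | Cohort 7 (Lugano) |
|---|---|---|---|
| Radiotherapy prohibited by default | applies | applies | applies |
| Need must not amount to progression | applies | applies | applies |
| Lesion is not a RECIST target lesion | protects the measured lesions | excludes nothing | excludes nothing |

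In cohort 7 the empty condition matters only when the irradiated site is the sole or most intense one. The five-point score follows the hottest initial site, so treating a minor site does not change it.

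**Step 2. Does another section close the gap?** Sections 7.2.8 and 7.2.8.1 to 7.2.8.3 and Appendices 3 and 4 contain no rule for an irradiated IPCG or Lugano lesion. The caution on previously irradiated lesions stands only in Appendix 1 (RECIST) and concerns baseline measurability. The non-responder rules do not mention permitted irradiation. Exclusion criterion 7 exempts the brain from the 21-day radiotherapy washout with no exception for cohort 3, so brain irradiation between baseline MRI and the first dose is not barred there either. Section 7.2.8.1 shows that the protocol can name both systems in a lesion rule: "In the event that the patient shows an increase in lesion size consistent with RECIST v1.1 or IPCG criteria for disease progression".

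**Step 3. Size per event.** The protocol states no figure on this point, so there is none to reproduce. One extra response in n patients adds 1/n to the ORR:
- n = 20: 1/20 = 5 points. For example, 2/20 = 10% (exact 95% CI 1.2 to 31.7) becomes 3/20 = 15% (3.2 to 37.9).
- n = 50: 1/50 = 2 points. Section 1.3 cites 4/11 = 36% for an anti-PD-1 antibody in diffuse large B-cell lymphoma. At that level, 18/50 = 36% (22.9 to 50.8) becomes 19/50 = 38% (24.7 to 52.8).
- n = 100, the bound if all 50 additional patients went to cohort 3: 1/100 = 1 point.

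**Step 4. Expected inflation, under assumption only.** Let f be the share of the cohort irradiated at an assessed, non-progressing lesion before Day 84, and r the share of those who become false responders. The inflation is f × r. Neither is in the protocol. With f from 1% to 5% and r from 25% to 100%, both assumed:
- lowest: 1% × 25% = 0.25 points
- r = 50%: 1% × 50% = 0.5 to 5% × 50% = 2.5 points
- highest: 5% × 100% = 5 points

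**Step 5. Could it change the 10-patient futility look?** Inputs: p0 = 0.10 (section 10.3), 85% confidence (synopsis, section E), and a Jeffreys or uniform prior (section 10.3 leaves the choice open).

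| Responses in 10 | P(p < 0.10), Jeffreys | P(p < 0.10), uniform |
|---|---|---|
| 0 | 0.858 | 0.686 |
| 1 | 0.439 | 0.303 |

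One false response could move the decision only under Jeffreys, and only from 0 to 1. At a true rate of 4/11, the chance of no response in 10 is (7/11)^10 = 0.011, or 1.1%. Under the uniform prior, 0/10 does not stop the cohort, so nothing changes.

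**The case against.** The strongest reply is that the scenario is narrow. Radiotherapy is banned by default, and the exception is discretionary and closed to progressing patients. In refractory PCNSL, a need to irradiate the assessed lesion will often be progression, and section 7.2.8 asks for extra imaging when symptoms suggest it. This stands. A reader might infer that the whole radiotherapy safeguard fails in cohorts 3 and 7. The text does not support that, because only the lesion condition is empty. The exception nevertheless presupposes symptomatic lesions that need palliation without progression, so the case is not excluded.

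Second, the closing sentence of 5.9.2 might be read as removing anyone who receives radiotherapy. It is ambiguous. On that reading the exception would permit nothing, so it is unlikely to be meant, but the text does not settle it.

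Third, the protocol uses RECIST loosely elsewhere: sections 3.2 and 7.2.8.1 both fall back on RECIST alone after naming other systems. A purposive reading of 5.9.2 would cover any lesion used for response assessment. That may well be the intention, and it weakens the contrast with 7.2.8.1. It does not tell a site treating a PCNSL patient what it may irradiate.

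Fourth, the IRC charter, which is not shown, may call an irradiated lesion non-evaluable, which already means non-responder. That would protect the final IRC analysis. It would not reach the interim looks, which use the investigator's assessment, nor the investigator-based results also reported at the end. Classification rules may properly sit in the SAP or the charter; which lesions may be irradiated is set by the protocol.

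**Conclusion.** The point holds in a limited form. In cohort 3, and in cohort 7 when the irradiated site is the sole or most intense FDG-avid site, the lesion condition of 5.9.2 excludes nothing. A permitted irradiation can therefore produce a Day-84 response that is credited to pembrolizumab. Each such case adds 5 points to the ORR at n=20 and 2 points at n=50, always upward.

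The frequency is unknown and should be low, because the default ban and the no-progression condition remain in force. The 0.25 to 5 point range rests wholly on assumed inputs and is not evidence of a material bias. At n=50 the 2-point shift lies well inside an interval about 28 points wide.

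A reader might infer that futility decisions are at risk. The documents do not support this: it would take exactly 0 against 1 response in 10 and the Jeffreys prior, and zero responses has about a 1% chance at the response rate cited for the related lymphoma. Nor does every irradiated site in cohort 7 matter. Severity: minor.

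**What to change.** In 5.9.2, after the reference to RECIST v1.1 target lesions, add: *nor a lesion used for response assessment under the cohort's own criteria (cohort 3: any enhancing brain, ocular or leptomeningeal lesion under IPCG, including within a brain field; cohort 7: the sole or most intense FDG-avid site of initial disease under Lugano)*.

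If such a lesion is irradiated all the same between baseline imaging and Day 84, classify the patient as non-evaluable at Day 84. The existing rule in 3.1.1 and 10.2.1 then makes that patient a non-responder. Apply this in both the investigator-based interim analyses and the IRC analysis. Whether to irradiate remains a clinical decision, and RECIST non-target lesions in the other five cohorts may be treated as now.

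Cost: one clause, one classification statement and one analysis flag. The ORR in cohorts 3 and 7 may be slightly lower, and an occasional genuine responder will be counted as a failure.
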